All drug compliance records will be kept current and will be made available for inspection by regulatory agency inspectors. Study drug will be given to patient at the baseline visit, and preferably at 6 month intervals thereafter. Instructions for shipping study drug to patients are provided in the appendix.

B.9. Study Timeline

There are two in-person study visits (baseline and 78 week follow-up) when patients will undergo vwMRI, approximately 60 minutes long, with a simultaneous clinical evaluation by a study investigator physician and blood draw. Every 2-4 months, the study coordinator will determine medication adherence, adverse events, or patient-reported recurrent stroke (see **Figure 1**).

	Screen/ Baseline	Day 1	Day 60	Day 120	Day 180	Day 240	Day 320	Day 480	Day 546
Informed Consent	Х								
Medical History/Current medications	х		х	х	х	Х	х	х	х
Vitals	Х								Х
Review CTA or MRA ¹	х								
Vessel wall MRI		Х							Х
Pregnancy test	Х								
Creatinine	Х								Х
Lipid panel	Х								Х
Lipoprotein (a)	Х								Х
Apolipoprotein B	Х								Х
Physical exam	Х								Х
Neurological exam	Х								х
NIHSS	Х								Х
Modified Rankin Scale	х								Х
Stroke adjudication			Х	Х	Х	Х	Х	Х	Х
Adverse event determination			х	Х	х	Х	х	х	х
Serious adverse events			Х	Х	Х	Х	Х	Х	Х

Figure 1: Schedule of Activities

1. To confirm ICAD of a major intracranial artery

B.10. Study Duration

- Estimated duration of research (study start to final study deliverable): 2 Years / 6 Months
- Estimated duration of first patient enrolled to last patient out: 2 Year / 0 Months
- Estimated duration for Amgen to supply study drug: 2 Year / 0 Months

C. Study Endpoints

C.1. Primary Endpoints

The primary endpoints are nominal change in the stenosis and percent atheroma volume (PAV) of cerebrovasculture arteries from baseline to week 78. We will use measure stenosis and PAV on vessel wall MRI (vwMRI), which evaluates all arteries from the aortic arch to the distal intracranial vasculature in a single scan. The primary endpoints will be analyzed for both: 1) all intra- or extracranial arteries that have at least 25% stenosis, and 2) seperately for the intracranial arteries. Stenosis and PAV will be measured using standard methodology.

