C.1.a. Primary endpoint measurement: All vwMRIs are on a 3T scanner with a 20- or 32-channel head coil and gadolinium. The field of view is from the aorta to the top of the skull. Sequences include the following for Siemens scanners and equivalents for Phillips and GE:

Sequence	3D ToF	DWI	3D FLAIR	3D MPRAGE	PD SPACE DANTE	3D SWI	T1 SPACE DANTE	T2 SPACE DANTE
Contrast (gadolinium)	Pre	Pre	Pre	Pre	Pre	Pre	Pre/Post	Post

DANTE = Delay Alternating with Nutation for Tailored Excitation (for blood suppression); DWI = Diffusion Weighted Imaging (Tensor technique); GRE = Gradient Recalled Echo; MPRAGE = Magnetization Prepared Rapid Acquisition Gradient recalled Echo; PD = proton density; SPACE = Sampling Perfection with Application optimized Contrasts using different flip angle Evolution; SWI = susceptibility weighted imaging (with quantitative susceptibility mapping); ToF = Time-of-Flight

At the completion of patient enrollment, two neuroradiologists will examine all vwMRIs in three separate viewing sessions to prevent viewer fatigue. They will be given a rater sheet directing them to record findings in the brain and all major vessels of the cerebrovasculature, including:

- a) Stenosis: will be identified by the luminal imaging component of the vwMRI protocol (MR angiography of the head and neck). Stenosis will documented on the NIH Stroke CDE "Vessel Imaging Angiography"²⁵ for all cerebrovasculature vessels from the aorta to distal intracranial vessels. Any vessel with >25% stenosis qualifies for computation of this composite outcome.
- b) Percent atheroma volume (PAV): We will use MRI-PlaqueView (VPDiagnostics, Seattle, WA) to measure PAV in the aortic arch, cervical carotid, cervical vertebral and all major intracranial arteries. MRI-PlaqueView is a powerful application that allows identification of (a) vessel lumen and outer wall (OW), (b) atheroma (both calcified and lipid rich). PAV is measured on the cross-sectional slice with the highest % stenosis. PAV = Σ(OWarea Lumenarea)/ΣOWarea × 1

C.2. Secondary endpoint 1

Secondary endpoint 1 is post-contrast plaque enhancement for intracranial arteries and intraplaque hemorrhage for the cartotid artery, which are determined by two experienced neuroradiologist raters. If there is disagreement, then a third rater serves as a tie-breaker. The signal intensity characteristics of both endpoints have been standardized in prior literature.

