We will fit a mixed effects linear regression model, specifically a LOESS smoothing curve, to change in stenosis/PAV and on-treatment LDL-C, HDL-C, and lipoprotein(a). We will also use a multivariable linear regression model with the outcome of the primary endpoints, adjusted for covariates that could be confounders such as age, gender, smoking, statin use/dose and relevant medical comorbidities. The primary endpoints will also be compared to an assumed value of 0% change in stenosis and PAV that would correspond to optimal medical management without a PCSK9 inhibitor. Although, some studies have suggested statin therapy can reduce carotid atherosclerosis, no such effect is known for ICAD. For this analysis, we will use linear mixed effects model to detect differences in the stenosis and PAV endpoints between patients taking Repatha or the presumed historical control values of 0% change. For the secondary endpoints, we will use logistic and linear regression depending on the nature of the variable and use the primary predictors of on-treatment LDL-C, HDL-C, and lipoprotein(a). For the exploratory endpoint of recurrent stroke, we will use the above mentioned methods as well as a Cox proportional hazards model for the endpoint of recurrent stroke with the observed rate in this study compared to controls matched according to degree to stenosis of the index artery. Due to differences in arterial structure and flow dynamics, there may be a more significant plaque reduction in certain intracranial vessels. We anticipate subgroup analyses, for example comparing change in stenosis or PAV in the middle cerebral artery versus the vertebral artery.

D.2. Power Analysis

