We power our study on the primary endpoint of change in stenosis and PAV. The GLAGOV trial showed 0.95% reduction in PAV for patients randomized to Repatha versus a 0.05% increase in PAV for patients in the placebo arm and was 78 weeks in length. Because the major intracranial arteries have a similar luminal diameter to coronary arteries, we may reasonably expect a 1% reduction in PAV for our 78 week study as documented in previous literature. Patients with intracranial atherosclerosis can be expected to have at least 3 additional sites of atherosclerosis, including extracranial arteries, that will be included in the series of PAV outcomes. Each subject will provide four sites of atherosclerosis and therefore, 4 PAV measurements. This cluster designed study will be modeled by a mixed effects linear regression to account for the cluster of arteries per patient. We obtain >80% power for our sample size of 150 patients, two-sided significance level 0.05, and a conservative assumed standard deviation of 4% from previous studies for the assumed 1% reduction in PAV against the documented control PAV of 0%.²³ With 150 patients, the minimum effect size possible to detect with 80% power is a 0.51% reduction. A 0.50% difference has been reported to be the cutoff to distinguish individuals that experience cardiovascular events versus those who do not.²³ Assuming a withdrawal rate of 25-30%, we would still reach >90% power for a 1% reduction with the above-listed conditions. We do not expect to show a significant reduction in recurrent stroke, but anticipate seeing a trend towards that outcome. This data could be used to accurately construct and power a subsequent trial with the primary outcome of recurrent stroke. Finally, in GLAGOV the linear relationship between change in stenosis, PAV and on-treatment LDL-C was very robust. We will be replicate this finding through means of a generalized linear mixed effects model. Our effective sample size may be sufficiently large enough to match the GLAGOV trial as each patient will be able to contribute an average of 4 arteries giving us an expected sample size between 800 and 1200 dependent on a conservative prediction of intra-class correlation. All reported p-values will be twosided and deemed significant at the 0.05 level.

D.3. Loss to Follow-up

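### The models linking change in stenosis/PAV to on-treatment lipids do not pre-specify artery location or the artery's baseline value, although both are recorded; the loss is modest and any confounding is possible, not shown

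*Combined protocol and SAP*

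**What the plan says.** Three kinds of model for change in stenosis or PAV appear in D.1 and D.2.

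- **Lipid models.** D.1 opens with a mixed effects regression ("specifically a LOESS smoothing curve, to change in stenosis/PAV and on-treatment LDL-C, HDL-C, and lipoprotein(a"). D.2 returns to the LDL-C relation reported by the coronary evolocumab trial: "We will be replicate this finding through means of a generalized linear mixed effects model". Neither passage names an adjustment covariate.
- **Multivariable model.** D.1 adds a linear regression of the primary endpoints, "adjusted for covariates that could be confounders such as age, gender, smoking, statin use/dose and relevant medical comorbidities". It does not say whether a lipid value is also in this model.
- **Comparison with no change.** "The primary endpoints will also be compared to an assumed value of 0% change in stenosis and PAV", by a linear mixed effects model, again with no covariates named.

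Both artery-level variables will be in the data. C.1 defines the outcome as "nominal change in the stenosis and percent atheroma volume (PAV) of cerebrovasculture arteries from baseline to week 78", so each analysed artery has a baseline value. C.1.a has the readers "measure PAV in the aortic arch, cervical carotid, cervical vertebral and all major intracranial arteries" and document stenosis vessel by vessel.

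Location is not ignored. C.1 analyses all arteries with at least 25% stenosis and then "seperately for the intracranial arteries". D.1 remarks that "there may be a more significant plaque reduction in certain intracranial vessels" and anticipates vessel subgroups. D.2 models the clustering of arteries within a patient.

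**The concern.** The pooled analysis combines very different lesions: the aortic arch, cervical carotid and vertebral arteries, and intracranial vessels. Stenosis runs from about 25% up to the 99% allowed for the index artery. Change may depend on the starting value and on the vessel. D.1 says the latter for intracranial vessels. It also notes that statins may reduce carotid atherosclerosis, with no such effect known for intracranial disease.

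Patient-level covariates cannot describe differences between arteries within a patient. If those differences predict change, leaving them out of the lipid models inflates the standard error of the slope. If artery mix or baseline severity is also associated with on-treatment LDL-C, the slope is biased.

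The LDL-C relation matters here. D.2 presents it as a planned replication, and C.3 uses the lipid changes to study mechanism. In a single-arm trial, LDL-C on treatment is not randomised, so the choice of adjusters should be fixed before the data are seen.

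**Working it through.** **Inputs from the plan (D.2).** 150 patients, 4 PAV measurements each, SD of change 4%, two-sided 0.05, effect 1%, claimed power above 80%, minimum detectable effect 0.51%. No intra-class correlation (ICC) is given.

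**Inputs assumed.** r, the correlation of change with baseline: 0.1 to 0.5. Standardised effect of baseline on change: −0.1 to −0.4. Correlation of baseline with on-treatment LDL-C: 0 to 0.3. The documents give none of these.

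**1. The plan's own figures.** With one measurement per patient, power = Φ(1/(4/√150) − 1.960) = Φ(3.062 − 1.960) = 86.5%. With 4 arteries, n_eff = 600/(1 + 3·ICC), and power is 97.2% at ICC 0.5. So the claim of more than 80% holds at any ICC from 0 to 1. The 0.51% figure needs n_eff = (2.8016 × 4/0.51)² = 483, a design effect of 600/483 = 1.243 and hence an ICC of 0.243/3 = 0.081. All of this uses the unadjusted SD of 4%, so none of it depends on the present point.

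**2. Precision of the lipid slope.** If baseline is unrelated to LDL-C, residual SD = 4·√(1 − r²), and the slope's standard error falls in proportion.

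| r | Residual SD | Fall in SE |
|---|---|---|
| 0.1 | 3.98 | 0.5% |
| 0.2 | 3.92 | 2.0% |
| 0.3 | 3.82 | 4.6% |
| 0.4 | 3.67 | 8.3% |
| 0.5 | 3.46 | 13.4% |

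This treats the measurements as independent. LDL-C is one value per patient, so what matters is the variance of the patient's mean over 4 arteries, proportional to ICC + (1 − ICC)/4. Take ICC 0.5 and r = 0.3.

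- Before adjustment: 0.5 + 0.5/4 = 0.625.
- Baseline explains only artery-level variation: 0.5 + (0.5 − 0.09)/4 = 0.6025, so the SE falls by 1 − √(0.6025/0.625) = 1.8%.
- Baseline explains only patient-level variation: (0.5 − 0.09) + 0.125 = 0.535, so the SE falls by 1 − √(0.535/0.625) = 7.5%.

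The 4.6% in the table lies between the two.

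**3. Possible bias if baseline truly drives change and is omitted.** Bias per SD of LDL-C = 4 × (baseline effect) × (correlation of baseline with LDL-C). This is 0 if that correlation is 0. In size it runs from 4 × 0.1 × 0.1 = 0.04 to 4 × 0.4 × 0.3 = 0.48 PAV points.

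**4. Possible bias if baseline is included but its correlation with change is only measurement error.** Suppose LDL-C has no effect and is unrelated to change. The unadjusted slope is then unbiased. With r = −0.3 and correlation c between observed baseline and LDL-C, the adjusted slope is 4 × 0.3c/(1 − c²): 4 × 0.03/0.99 = 0.12 at c = 0.1, and 4 × 0.09/0.91 = 0.40 at c = 0.3. If the 0.1 to 0.3 refers to the error-free baseline, simulation gives about 0.11 to 0.34. Steps 3 and 4 are of similar size, so the baseline term can remove bias or create it.

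**5. Comparison with 0%.** The mean change is the same with or without a centred baseline. In a simulation with n = 150 and 20,000 runs, its true sampling SD at r = 0.3 is 0.326 (4/√150 = 0.327), but the centred model reports 0.311. Nominal 95% intervals from that model cover 93.9% at r = 0.3 and 91.5% at r = 0.5. Unadjusted intervals cover 94.9% and 95.2%. Baseline adjustment brings no gain here and understates the error.

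**The case against.** The covariate list is introduced as examples, so it excludes nothing. A reader might infer that the plan has decided to leave out baseline and location, but the text supports only that they are not pre-specified. The listed covariates also belong to the multivariable model, which may not contain LDL-C. The evidence on the lipid models is that they name no adjusters.

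Location is partly handled by the separate intracranial analysis, the vessel subgroups and the clustering by patient. That stands, but none of these adjusts the pooled lipid slope for artery mix. The intracranial analysis still pools different vessels, and a patient-level random effect does not account for measured differences between arteries.

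A reader might also infer that the LDL-C slope is confounded by baseline severity. The documents do not support that. It would require baseline severity to be associated with on-treatment LDL-C, and they are silent on this.

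The strongest objection is that baseline adjustment of a change score is not a free gain when the exposure is not randomised. Step 4 bears this out, and it is why the slope without the baseline term must also be reported. It applies less to location, where which vessel was measured is not subject to that kind of error.

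Finally, adjusting every model for change would be wrong. Step 5 shows the harm to the comparison with 0%. Nor would adjustment remove regression to the mean caused by selecting stenosed arteries.

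**Conclusion.** The point holds as a gap in pre-specification, limited to the models relating change in stenosis or PAV to lipids and covariates. Artery location and baseline value are recorded, at least location is expected by the plan to matter, and neither is a planned term.

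The cost in precision is modest: about 0.5% to 13% of the slope's standard error for an assumed r of 0.1 to 0.5, smaller if baseline explains mainly artery-level variation and larger if it explains mainly patient-level variation. Confounding of the slope is possible and not demonstrated. Under the stated assumptions, omitting baseline could bias the slope by anything from 0 to 0.48 PAV points per SD of LDL-C. The bias figures are for PAV only, since the plan gives no SD for change in stenosis.

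A reader might infer that the trial's power or its comparison with 0% is weakened. Neither follows: the power figures use the unadjusted SD, and that comparison gains nothing from adjustment. This is a worthwhile refinement, not a flaw that threatens the trial.

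**What to change.** In D.1, state that the mixed models relating change in stenosis or PAV to LDL-C, HDL-C, lipoprotein(a) and covariates include, as fixed effects, artery location (intracranial, carotid, vertebral, aortic) and the artery's centred baseline value of the measure being analysed, with a random intercept for patient to carry the clustering already planned in D.2. In the intracranial-only analysis that four-level factor does not vary, so the individual vessel would take its place.

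State also that:

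- the lipid slope without the baseline term is reported as a sensitivity analysis, because baseline is measured with error;
- the comparison with 0% remains the unadjusted mean change, with clustering by patient.

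The cost is one further sensitivity analysis and a few model degrees of freedom. No new data are needed, and the sample size and power statements stay as they are.

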culprit lesions.²² The combination of stenosis + atheroma burden + luminal area produced an odds ratio of 3.99 (95% CI: 1.74-9.13, p=0.001) for culprit plaque. The GLAGOV study showed that PCKS9 inhibition reduced the percent atheroma volume of coronary arteries over a 78 week treatment period.²³ With atheroma volume now established as a viable biomarker, vwMRI is the optimal test to monitor it and stenosis, both for ICAD and in other locations of the cerebrovasculature, such as the carotid arteries, cervical vertebral arteries, and aortic arch.

A.5. Impact

The result of this study will be a dataset that lays the foundation for a randomized controlled trial of Repatha in ICAD patients. The data collected in this study will allow us to optimize a future clinical trial designed to demonstrate a reduction in stroke risk, ultimately making more efficient and economical progress towards our ultimate research goal of preventing stroke with Repatha. While we are proposing future studies to reduce ICAD stroke risk, it should be noted that our study will also evaluate the potential for Repatha to decrease cerebrovasculature stenosis and plaque burden, which would be a compelling primary prevention indication.

B. Approach

B.1. Study Hypothesis

We hypothesize that inhibition of PCSK9 with Repatha in patients with moderate to severe intracranial atherosclerosis will reduce validated biomarkers of stroke risk (stenosis and percent atheroma volume). To answer our hypothesis, we propose a single arm study of Repatha in 150 patients with a prior history of ischemic stroke and ICAD causing at least 50% stenosis of a major intracranial artery in the Circle of Willis ("index artery").

B.2. Study Design

We will enroll 150 ICAD patients with a prior history of ischemic stroke. Patients will be enrolled at up to 8 medical centers in North America. All patients will receive Repatha for 78 weeks and will have an MRI before beginning study medication and a comparison MRI immediately after completing study medication.

B.3. Investigational Treatment

The investigational treatment is Repatha 140 mg administered subcutaneously with a single-dose pre-filled pen syringe every 2 weeks for a total of 39 treatments. Dose modification is not allowed.

B.3.a. Inclusion Criteria

- Adult patients, ≥ 18 years of age

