- History of ischemic stroke, defined as an episode of neurological dysfunction caused by focal cerebral, spinal, or retinal infarction (American Heart Association definition).
- Large vessel atherosclerosis of an intracranial artery in the circle of Willis with 50-99% stenosis by WASID criteria (percent stenosis = (1-[diameter stenosis/diameter normal]) x 100%) on MRA, CTA or DSA
 - Eligible arteries: vertebral (V4), basilar, PCA (P1, P2), MCA (M1, M2), tICA, ACA (A1)
- Current statin use or contraindication to statin
- Fasting LDL-C ≥ 70 mg/dL or LDL-C ≥ 60 mg/dL if lipoprotein (a) > 30 mg/dL; within a year of randomization and on the current statin medication/dose

B.3.b. Exclusion Criteria

- Gadolinium or PCSK9 inhibitor allergy
- Acute or chronic kidney disease with eGFR<30 ml/min/1.73m²
- Pacemaker or other MRI contraindications per American College of Radiology guidelines²⁴
- Inability to return for 78 week follow-up clinic visit and vwMRI

Pregnant at time of enrollment

B.4. Investigational New Drug Status

We will not require an IND. Repatha is indicated to reduce the risk of myocardial infarction, stroke, and coronary revascularization in adults with established cardiovascular disease; and as an adjunct to diet, alone or in combination with other lipid-lowering therapies (e.g., statins, ezetimibe), for treatment of adults with primary hyperlipidemia to reduce low-density lipoprotein cholesterol (LDL-C). Our patient population meets these criteria given 1) history of ischemic stroke and 2) presence of moderate to severe ICAD.

B.5. Patient Recruitment

Patients will be approached first by a member of their clinical care team in order to gain permission for a study member to approach to discuss the study in detail. Only co-investigators or study coordinators on this study will consent patients. Standard consenting procedures will be followed, including giving patients and family members adequate time to discuss the study with the study team and amongst themselves prior to consenting. A full, written, IRB- approved Informed Consent document will be provided to the patient (or representative) for signature after the patient or patient's representative has had time to read it and ask questions. A copy will be given to the patient for his/her records. Proxy consent by legally authorized representatives will be allowed in the case of post-stroke aphasia or other cognitive disability, in order to not bias study entry by stroke severity.

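### The plan justifies the 0% reference for intracranial disease only but also applies it to a pooled primary set that includes carotid arteries, so a significant pooled fall cannot be credited to Repatha alone

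*Combined protocol and SAP*

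**What the plan says.** The design has no concurrent control (B.1): "we propose a single arm study of Repatha in 150 patients". In its place, D.1 has the primary endpoints "compared to an assumed value of 0% change in stenosis and PAV that would correspond to optimal medical management without a PCSK9 inhibitor". The linear mixed model for this comparison uses "presumed historical control values of 0% change", one value for every artery.

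The next statement in D.1 gives the only argument for 0%: "some studies have suggested statin therapy can reduce carotid atherosclerosis, no such effect is known for ICAD".

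C.1 defines two analysis sets for each primary endpoint: "1) all intra- or extracranial arteries that have at least 25% stenosis, and 2) seperately for the intracranial arteries". C.1.a shows what the first set can contain, since the software will "measure PAV in the aortic arch, cervical carotid, cervical vertebral and all major intracranial arteries". Among the inclusion criteria (B.3.a) is "Current statin use or contraindication to statin", so most patients will be on a statin.

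The documents give no separate reference for carotid or other extracranial arteries, no ranking of the two sets, and no sensitivity analysis over other reference values.

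**The concern.** With no control arm, the reference value stands in for what would have happened without Repatha. D.1 raises a doubt about that value for carotid arteries and answers it only for intracranial arteries. The pooled set nevertheless uses the same 0% for both. If carotid plaque shrinks somewhat on statin alone, the pooled mean falls below zero with no contribution from Repatha, and the test counts that fall as a drug effect.

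The exposed analysis is also the one behind the sample size: D.2 counts four sites per patient and says that they include extracranial arteries. A.5 presents the data as the foundation for a randomized trial, so an inflated effect would carry over into that trial's design.

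**Working it through.** **Inputs from the documents (D.2).** 150 patients; four PAV sites per patient; SD 4%; two-sided 0.05; expected reduction 1%; minimum detectable effect 0.51% at 80% power; withdrawal 25-30%, and 30% leaves 150 x 0.70 = 105 completers.

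**Inputs the documents do not give (assumed).** The share *s* of sites that are carotid (1/4 or 2/4); the statin-only carotid PAV change *r* (-0.5 or -1.0 points); the ICC between sites in one patient.

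**Step 1: the plan's own figures.** I use a one-sample normal approximation against a fixed value, with SE = 4/sqrt(n_eff) and n_eff = 4n/(1 + 3 x ICC).
- Power with one value per patient (n_eff = 150): SE = 4/sqrt(150) = 0.327; Phi(1/0.327 - 1.960) = 86.5%. This agrees with the stated figure of more than 80%.
- Minimum detectable effect 0.51: n_eff = (2.802 x 4/0.51)^2 = 483. The design effect is 600/483 = 1.243, so ICC = 0.243/3 = 0.081. The plan does not state this value; it is what makes 0.51 come out. I therefore also show ICC 0.5.

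**Step 2: standard error with 105 completers (420 sites).**
- ICC 0.081: n_eff = 420/1.243 = 338; SE = 4/sqrt(338) = 0.218.
- ICC 0.5: n_eff = 420/2.5 = 168; SE = 4/sqrt(168) = 0.309.

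**Step 3: chance of a significant result if Repatha adds nothing.** The pooled mean is then b = s x r, with no change assumed at the other sites. The chance is Phi(|b|/SE - 1.96) + Phi(-|b|/SE - 1.96).

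| Carotid sites | r | b | ICC 0.081 | ICC 0.5 |
|---|---|---|---|---|
| 1 of 4 | -0.5 | -0.125 | 8.9% | 6.9% |
| 1 of 4 | -1.0 | -0.25 | 21.0% | 12.8% |
| 2 of 4 | -0.5 | -0.25 | 21.0% | 12.8% |
| 2 of 4 | -1.0 | -0.50 | 63.2% | 36.7% |
| any | 0 | 0 | 5% | 5% |

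For example, with b = -0.25 and ICC 0.081, 0.25/0.218 = 1.149 and Phi(1.149 - 1.96) is about 0.21; the second term is negligible. With all 150 patients the ICC 0.081 column becomes 10.6%, 27.9%, 27.9% and 78.4%. More patients make this worse, because the shift does not shrink with the SE.

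**Step 4: whether other parts of the plan remove the problem.**
- The adjustment for statin use and dose in D.1 belongs to a separate regression. Every patient receives Repatha, so no data show the change without it.
- The placebo-arm change of +0.05% cited in D.2 is coronary. D.2 extends the coronary result to intracranial arteries through similar luminal diameter and makes no such argument for carotids.
- The subgroup analyses in D.1 are only anticipated, and the example given is middle cerebral versus vertebral artery.

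**The case against.** The strongest reply is that the intracranial question already has its own primary analysis, which this problem does not touch on the plan's premise. The pooled set serves another stated aim (A.5), plaque burden across the cerebrovasculature. This stands, and it narrows the point to attribution in the pooled set and to the risk of claiming success on that set alone.

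The second reply is that nothing in the documents supports a carotid statin effect of -0.5 to -1.0. The upper end equals the whole effect expected from Repatha. B.3.a requires the qualifying LDL-C to be measured on the current statin and dose, so patients enter on established treatment or with a contraindication, and further statin regression may be small. The one statin-treated control figure, +0.05%, is close to zero. This also stands as regards size. It does not supply the missing justification, because that figure is coronary and D.1 itself raises the carotid doubt.

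Third, a fixed reference without uncertainty is common to all single-arm tests. That is true. What is specific here is that the stated justification covers only part of the set tested.

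A reader might infer more than the documents support:
- That the false-positive chance is 21% to 63% in general. That range needs two of four sites to be affected and an unstated ICC of about 0.08.
- That vertebral and aortic arch sites share the statin effect. D.1 concedes it for carotid disease only.
- That the pooled test must be dropped or a control arm added. By-bed reporting and a sensitivity table deal with the attribution problem without either.

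**Conclusion.** The inconsistency is real and can be read directly from the plan: 0% is defended for intracranial disease and also applied to a set that may include carotid arteries in mostly statin-treated patients. A significant pooled fall from 0% therefore does not by itself show a Repatha effect. The intracranial analysis is unaffected on the plan's premise, but nothing says that it is the deciding one.

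The size is unknown. Over the assumed range the chance of a false significant PAV result with 105 completers runs from about 7% to 63%, and it stays at 5% if statins do nothing further to the carotids. Stenosis is tested against the same 0% and has the same gap; it is not quantified here because D.2 gives its SD and effect for PAV only. This is a cheap improvement worth making, not a flaw that invalidates the trial.

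**What to change.** In D.1:
1. Name the intracranial set as the one on which the claim against 0% rests.
2. Keep the pooled comparison, but label it as not attributable to Repatha alone.
3. Report mean change with 95% CI by bed: intracranial, carotid, other extracranial.
4. Add a sensitivity table over reference values for PAV (for example 0 to -0.5 points) and a similar one for stenosis, and state the value at which significance is lost.

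The value in item 4 is the upper 95% confidence limit of the mean change. If the planned fall of 1 point were observed in 105 completers, it would be -1.0 + 1.96 x 0.218 = -0.57 at ICC 0.081, and -1.0 + 1.96 x 0.309 = -0.39 at ICC 0.5. The table could therefore strengthen the pooled result as well as weaken it.

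Cost: a little more analysis, a weaker pooled claim, and a main claim that rests on fewer arteries. If two of four sites are intracranial, with 105 completers and ICC 0.081, n_eff = 210/1.081 = 194 and the PAV minimum detectable effect is 2.802 x 4/sqrt(194) = 0.80 points. With all four sites it is 2.802 x 0.218 = 0.61. No extra patients or scans are needed.
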